10.6 SAFETY ANALYSIS

The safety analysis will be based on the SAF. This includes reported AEs and other safety information (ie, clinical laboratory evaluations and vital signs). A summary of safety results will be presented for each treatment group.

10.6.1 Analysis of Adverse Events

Adverse events reported in this study will be coded using the currently available version of MedDRA. Coding will be to lowest level terms. The verbatim text, the PT, and the primary SOC will be listed in patient listings.

Pre-treatment AEs are defined as those that develop or worsen in severity from the time the patient provides informed consent, prior to the first dose of study drug. Treatment emergent AEs (TEAEs) are defined as AEs that develop or worsen in severity following the first dose of study drug through the last study visit.

The number and percentage of patients experiencing AEs and TEAEs will be summarized by seriousness (SAEs), severity (grades 1-5), SOC, and PT.

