11.5 Data Protection and Confidentiality	
11.6 Study Report and Publications	
11.7 Study Files and Retention of Records	
11.8 Case Report Forms	
11.9 Drug Accountability	
11.10 Inspections	
11.11 Access to Information for Monitoring	
11.12 Study Discontinuation	
REFERENCES	

Basic Information

STUDY TITLE: A Phase II, Open Label, Dose Escalation Study of Bermekimab (MABp1) in Patients with Moderate to Severe Atopic Dermatitis

INVESTIGATIONAL PRODUCT:	Bermekimab (MABp1)
IND NUMBER:	112,459
PROTOCOL NUMBER:	2018-PT044
PROTOCOL VERSION / DATE:	3.0/ 22 August 2018
SPONSOR:	XBiotech USA, Inc. [name] U.S.A. [contact]
SPONSOR'S MEDICAL OFFICER:	[name] M.D., MBA XBiotech USA, Inc. [name] U.S.A. [contact]
STUDY CHAIR	[name] [name]

Investigator/Sponsor Signatures

STUDY TITLE: A Phase II, Open Label, Dose Escalation Study of Bermekimab (MABp1) in Patients with Moderate to Severe Atopic Dermatitis

STUDY PRINCIPAL INVESTIGATOR SIGNATURE:

I have read the protocol and appendices. I understand the contents and intend to comply fully with all requirements and the applicable current local and international regulations and guidelines. No changes will be made without formal authorization by XBiotech USA, Inc., in the form of a protocol amendment.

INVESTIGATOR SIGNATURE:

Printed name of Investigator

Signature

Date

SPONSOR SIGNATURE: XBiotech USA, Inc.

[name] M.D., MBA, Medical Director

Signature

Date

Clinical Protocol Synopsis

Study Title: A Phase II, Open Label, Dose Escalation Study of Bermekimab (MABp1) in Patients with Moderate to Severe Atopic Dermatitis
Sponsor:
XBiotech USA, Inc.
Study Chair:
[name] M.D
Sample Size:
29 Subjects

Approximate Duration: The study duration of subject participation is approximately 10 weeks, including a 2 week screening period, a 7 week treatment period, and 1 week follow up period.

Study Objectives:

Primary Endpoint(s):

• Safety and Tolerability

Secondary Endpoints:

- Change in Eczema Area and Severity Index Score (EASI) from baseline to visit 8
- Assessment of Pharmacokinetics (PK)
- Patients (%) achieving Investigator's Global Assessment (IGA) Response (0 or 1) at visit
 8
- Patients (%) achieving ≥2 IGA Score Reduction at visit 8
- Change (%) for peak weekly averaged pruritus and pain numerical rating scores (NRS) from baseline to visit 8
- Change in weekly averaged peak NRS from baseline to visit 8

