2.9 CONCOMITANT MEDICATIONS AND PROCEDURES

Any treatment (including nutritional supplements) or procedure administered from the time of consent to the end-of-study visit (visit 9) is considered concomitant and will be recorded in the case report form (CRF). This includes permitted medications ongoing at the time of consent and throughout the study. Concomitant procedures are allowed with the exception of those listed in section 2.9.1.

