3. STUDY DESIGN AND OBJECTIVES

Phase 2, open label, dose escalation study of two dose cohorts of bermekimab in patients with moderate to severe atopic dermatitis. The study is multicenter, and will consist of two dose levels: Bermekimab administered subcutaneously at a dose of 200 mg weekly (4 doses) and bermekimab administered subcutaneously at a dose of 400 mg weekly (8 doses). Patients taking the 200mg dose will be followed for 5 weeks (6 visits, day 35 ± 20 , and patients taking the 400mg dose will be followed for 8 weeks (9 visits, day 56 ± 20) to allow for assessment of safety and preliminary efficacy.

Dose escalation details can be found in Section 5.3.

The protocol of the study will be approved by the Institutional Review Board (IRB) or the Ethics Committee (EC) of the participating study sites. Depending on the participating countries, both local and central IRB/EC approvals will be granted. The study will be registered at www.clinicaltrials.gov before the enrollment of the first patient. The trial will be conducted in compliance with the protocol, GCP, and all applicable regulatory requirements.

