5. TREATMENT PLAN

5.1 STUDY PROCEDURES

Screening

The screening period begins once the informed consent is signed (Max 14 days).

- Informed Consent
- Demographics
- Medical History
- Concomitant Medications/Treatments
- Physical Examination
- Vital Signs (blood pressure, pulse, oxygen saturation, respiratory rate and body temperature)
- Height
- Weight
- Body Mass Index (BMI) [BMI= weight (kg)/height (m²)]
- EASI
- IGA
- SCORAD
- Blood Draw, 21mL:
 - Chemistry panel: Albumin, Alkaline Phosphatase, ALT, AST, GGT, Bicarbonate (CO2) Calcium, Chloride, Creatinine, Glucose, Potassium, Sodium, Total Bilirubin, Total Protein, Urea Nitrogen, 8.5 mL blood
 - Hematology Panel: Complete Blood Count (CBC) with differential and platelets, 4.0 mL blood
 - Infectious disease screening: HIV antibody, Hepatitis C antibody, Hepatitis B panel (HBsAg, anti-HBc, anti-HBs), and interferon gamma release assay (IGRA), 8.5 mL blood
 - Serum pregnancy test for WOCBP, 8.5 mL blood
- Pruritus/Pain NRS: the baseline level of itching and pain will be recorded. Patients will be given a study diary that has the NRS (0-10 scale) for days 0 to 35. The patient will be instructed to complete the scale daily (three questions, each on a 0-10 scale). The patient should bring this diary to all subsequent visits for review by the site staff.

Visit 1 (Day 0)

> At least 45 minutes before injection: When using pre-filled syringes, remove syringe from

refrigeration and lay flat; allow to warm to room temperature. Do not heat

Pre-injection

- o Concomitant medications/treatments
- o Urinalysis
- Electrocardiogram (ECG) (patient should be supine for at least 5 minutes prior to performating ECG)
- o DLQI
- Urine pregnancy
- o EASI
- o IGA

- HADS
- Pruritus/Pain NRS: data from patient diary to be recorded at this time if available
- o SCORAD
- POEM
- o GISS
- Blood draw:
 - PK and Biomarker Analysis, 6mL
- Visit 1 Questionnaire, Part 1: Pruritus, Pain and Erythema
- Vital signs (blood pressure, pulse, oxygen saturation, respiratory rate and body temperature)

Bermekimab subcutaneous injection in accordance with injection site determined by BMI at Screening

Post bermekimab subcutaneous injection

- ➤ 1 hour monitoring post-injection
 - Injection reaction
 - Vital signs (blood pressure, pulse, oxygen saturation, respiratory rate and body temperature) one hour post injection (70 +/- 10 minutes)

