The SCORAD is a validated tool used in clinical research and clinical practice that was developed to standardize the evaluation of the extent and severity of AD. There are 3 components to the assessment: A = extent or affected body surface area, B = intensity, and C = subjective symptoms. The extent of AD is assessed as a percentage of each defined body area and reported as the sum of all areas, with a maximum score of 100% (assigned as "A" in the overall SCORAD calculation). The intensity of 6 specific symptoms of AD (redness, swelling, oozing/crusting, excoriation, skin thickening/ lichenification, dryness) is assessed using the following scale: none (0), mild (1), moderate (2), or severe (3) (for a maximum of 18 total points, assigned as "B" in the overall SCORAD calculation). Subjective assessment of itch and sleeplessness is recorded for each symptom by the patient or relative on a VAS, where 0 is no itch (or sleeplessness) and 10 is the worst imaginable itch (or sleeplessness), with a maximum possible score of 20. This parameter is assigned as "C" in the overall SCORAD calculation. The SCORAD is calculated as: A/5 + 7B/2 + C where the maximum is 103.

Patient Assessment of Pruritus and Pain

The NRS is a simple assessment tool that patients will use to report the intensity of their pruritus (itch) and pain during a daily recall period using a study diary. Patients will be asked to complete the following questions:

- For average itch intensity: "On a scale of 0 to 10, with 0 being 'no itch' and 10 being the 'worst itch imaginable', how would you rate your itch **on average** during the previous 24 hours?"
- For maximum itch intensity: "On a scale of 0 to 10, with 0 being 'no itch' and 10 being the 'worst itch imaginable', how would you rate your itch at the **worst moment** during the previous 24 hours?"
- For pain intensity: "On a scale of 0 to 10, with 0 being 'no pain' and 10 being the 'most severe pain', how would you rate your pain **on average** during the previous 24 hours?"

Patients will be instructed to record their NRS score daily from day 0 to day 56 (+/-2). Sites will be expected to review the diary at each visit and enter the data from the previous 7 days.

Visit 1 Questionnaire for Pruritus, Pain and Erythema

The following questions assess the intensity of pruritus (itch) and pain experienced by the patient before and after the injection of bermekimab during visit 1. The patient will answer the following questions:

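### Chemistry and hematology have no scheduled value that meets the plan's only baseline definition, and Group A's adverse event window is stated inconsistently

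*Combined protocol and SAP*

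**What the plan says.** **Laboratory baseline.** Section 10.6.2 plans summaries of each laboratory result and its change from baseline, by treatment group. Section 10 refers to Section 8 for the analysis variables. The only baseline definition is in Section 8.1: the assessment made at visit 1 before the injection. Under Section 10.5.1 a baseline that is not available stays missing. In Sections 5.1 and 5.2, chemistry and hematology are drawn at screening and at visits 3, 5 and 8. The visit 1 draw is for PK and biomarkers only.

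**Adverse event window.** Section 10.6.1 counts an event as treatment-emergent when it develops or worsens "following the first dose of study drug through the last study visit". The planned summary is: "The number and percentage of patients experiencing AEs and TEAEs will be summarized by seriousness (SAEs), severity (grades 1-5), SOC, and PT".

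Section 3 separates the groups: "Patients taking the 200mg dose will be followed for 5 weeks (6 visits, day 35" for Group A, and "patients taking the 400mg dose will be followed for 8 weeks (9 visits, day 56" for Group B. Other sections do not:
- Sections 7 and 9.3 run event monitoring and recording from visit 1 to visit 9.
- Section 2.9 collects treatments given up "to the end-of-study visit (visit 9) is considered concomitant".
- The Synopsis gives one duration for everyone: "a 2 week screening period, a 7 week treatment period, and 1 week follow up period".
- The Section 5.2 calendar is a single schedule to day 56.

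Section 9.3 adds that for a subject who leaves before visit 9, recording stops a week after the final injection.

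**ECG.** ECGs are scheduled at visit 1, before injection, and at visit 8.

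**The concern.** Safety and tolerability is the only primary endpoint, so the safety tables are the main result of the trial. Two of their inputs are not pinned down.

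A programmer who follows the text would produce an empty table of chemistry and hematology changes. One who improvises would have to choose between the screening panel and the first on-study panel at visit 3, which is taken after two injections. The plan does not make that choice.

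The crude percentage of patients with an event rises with time observed. If Group A is observed for less time than Group B, the two columns of the event table answer different questions, and a pooled column describes no single period. The wording also allows a case in which Section 9.3 stops requiring Group A's events to be recorded at day 28, while Section 10.6.1 counts them to day 35.

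**Working it through.** **1. Laboratory baseline: schedule against definition**

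| Time | Chemistry | Hematology | PK/biomarker |
|---|---|---|---|
| Screening (up to 14 days) | yes | yes | no |
| Visit 1, day 0, pre-injection | no | no | yes |
| Visits 3, 5, 8 (days 14, 28, 49) | yes | yes | yes |

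The definition requires a visit 1 value, and neither the 15 listed chemistry analytes nor the hematology panel has one. With the missing-baseline rule, the number of patients with a computable change is 0 of 9 + 20 = 29. Vital signs and urinalysis are taken at visit 1 before injection and are not affected.

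**2. Adverse event window: reproducing the stated days**

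Visits are weekly from day 0, so day = 7 × (visit − 1).
- Visit 6: 7 × 5 = 35. Visit 9: 7 × 8 = 56. Both agree with Section 3.
- Group A's last injection is at visit 4: 7 × 3 = day 21. The Section 9.3 clause then gives 21 + 7 = day 28, if a planned end at visit 6 counts as leaving before visit 9.
- Group B's last injection is at visit 8, day 49, and 49 + 7 = 56, so the clause leaves a completer's window unchanged.

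Follow-up per patient, Group B to Group A: 56/56 = 1.0, 56/35 = 1.6 or 56/28 = 2.0.

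**3. What unequal windows would do**

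The documents give no event rate for this population, so the risks here are assumptions. Assume the same constant hazard in both groups, hence no dose effect, and let p be the risk by day 35. Risk by day d = 1 − (1 − p)^(d/35).

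| p at day 35 | Day 56 | Gap (points) | Gap if hazard halves after day 35 |
|---|---|---|---|
| 5% | 7.9% | 2.9 | 1.5 |
| 10% | 15.5% | 5.5 | 2.8 |
| 30% | 43.5% | 13.5 | 7.1 |
| 50% | 67.0% | 17.0 | 9.4 |

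For the last column the exponent is 1 + 0.5 × 21/35 = 1.3. The gap is 0 if no first events occur after day 35, or if Group A runs to day 56.

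At p = 30%:
- Pooled figure: (9 × 0.300 + 20 × 0.435)/29 = 39.3%, which is neither the 35-day nor the 56-day risk.
- Day 28 reading: 1 − 0.7^(28/35) = 24.8% against 43.5%, a gap of 18.7 points.

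**4. Sampling error for comparison**

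One patient is 1/9 = 11.1 points in Group A and 1/20 = 5.0 points in Group B. The exact 95% interval for 3 of 9 is about 7% to 70%.

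**5. Would a common window help?**

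Both groups have four scheduled injections before visit 5, which falls on day 26 to 30. At p = 30%, the worst case (all of one group at day 26, all of the other at day 30) is 23.28% against 26.34%. That is 3.1 points instead of 13.5.

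**The case against.** **On the laboratory baseline.** The baseline sentence closes a paragraph on demography and atopic dermatitis, and may never have been meant for safety laboratories. That is a fair reading, but it leaves no laboratory baseline rule at all, so the gap stands either way. Section 10 calls itself the basis for the SAP, and a fuller SAP could supply the rule; nothing in these documents shows that it does. A reader might also infer that pre-dose laboratory data are lost. They are not: the screening panel exists, and only the rule for using it is missing.

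**On the event window.** The regimens differ by design in dose and number of injections, so Group B's extra time is largely on treatment and part of what is being described. No test is planned (Section 10.1), escalation rests on a separate sponsor review (Section 5.3), and Section 10.7.1 already tabulates exposure by group. All of this stands and limits the weight of the point. Tabulating exposure does not, however, align the event percentages.

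A reader might infer that a higher percentage at 400 mg would necessarily be an artefact of follow-up. The documents do not support that: if Group A is followed to day 56, only a wording conflict remains. Pooling is also conditional. Section 10.5 pools all analyses in general terms, while Section 10.6 mentions only results by group.

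**Conclusion.** The laboratory point holds as the plan is written: either 0 of 29 patients have a chemistry or hematology change from baseline, or no laboratory baseline is defined. It rests on the schedule and the definition alone, with no assumed rates.

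The window point is a definite inconsistency with a conditional consequence. Group A's window reads as day 35, day 56 or possibly day 28. If it is shorter than Group B's, percentages by group mix follow-up length with regimen, by 2.9 to 17.0 points at day 35 under the assumed risks and an equal constant hazard. That is smaller than the sampling error with 9 and 20 patients, and it affects how descriptive tables are read, not a test or the escalation decision.

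A third point follows only if Group A is confirmed to end at visit 6: Group A would then have no scheduled post-dose ECG.

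**What to change.** 1. **Section 10.6.2.** Define the safety laboratory baseline as the last value before the first injection, which for chemistry and hematology is the screening panel. List the days from that draw to first dose. Cost: one sentence and one listing column. Downside: the baseline can be up to about 14 days old.
2. **Event window.** Reconcile the Synopsis duration and Sections 2.9, 3, 5.2, 7, 9.3 (including its early-termination clause) and 10.6.1, and state one adverse event window per group in 10.6.1. Which schedule is right is for the sponsor to settle. Cost: clarifying wording.
3. **Only if the windows differ.** Label each event table with its follow-up length. Add one treatment-emergent table by group for events with onset before visit 5 (about day 28, four scheduled doses in both groups). Say that its length varies with the ±2 day visit window, and that it is descriptive and not a dose comparison, because the cohorts are sequential and non-randomized. Cost: one extra table from data already collected.
4. **Only if Group A ends at visit 6.** Label the ECG summary to say that Group A has no scheduled post-dose ECG. Cost: a table label.

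None of these changes needs a new assessment.

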- Change in SCORing Atopic Dermatitis (SCORAD) score from baseline to visit 8
- Patients (%) achieving 50% or greater reduction in EASI Score from baseline at visit 8
- Patients (%) achieving 50% or greater reduction in SCORAD Score at visit 8
- Change (%) in Patient Oriented Eczema Measure (POEM) Scores from baseline to visit 8
- Changes in Global Individual Signs Score (GISS) from baseline to visit 8
- Change from baseline to visit 8 in Dermatology Life Quality Index (DLQI)
- Change from baseline to visit 8 in Hospital Anxiety Depression Scale (HADS)

• Change (%) from pre- and post- injection of Visit 1 Questionnaire for pruritus, pain and erythema

Trial Design:

Phase 2, Open label, Dose Escalation Study of Bermekimab (MABp1) in Patients with Moderate to Severe Atopic Dermatitis.

Group A (n=9): patients will receive a total of 4 X 200mg subcutaneous injections of bermekimab. Dosing will occur weekly from visit 1 to visit 4.

Group B (n=20): patients will receive a total of 8 X 400mg subcutaneous injections of bermekimab. Dosing will occur weekly from visit 1 to visit 8.

Inclusion Criteria: No waivers/exemptions will be granted for protocol inclusion/exclusion criteria.

Subjects are included in the study if they meet all of the following criteria:

- Written informed consent provided by the patient
- Age ≥ 18 years
- Chronic Atopic Dermatitis present for at least 3 years
- Disease is not responsive to topical medications, or for whom topical treatments are not indicated or desired
- Willing and able to comply with all clinic visits and study-related procedure
- EASI score ≥ 16 at screening and baseline visits
- IGA score \geq 3 at screening and baseline visits
- $\geq 10\%$ body surface area (BSA) of AD involvement at screening and baseline visits
- Documented recent history (within 6 months before the screening visit) of inadequate response to treatment with topical medications or for whom topical treatments are otherwise medically inadvisable or undesired

Exclusion Criteria:

Subjects with ANY of the following will be excluded from the study:

- Treatment with an investigational drug within 8 weeks of baseline visit
- Having received the following treatments within 4 weeks before the baseline visit, or any condition that, in the opinion of the investigator, is likely to require such treatment(s) during the first 4 weeks of study treatment:

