3.1 STUDY ENDPOINTS

Primary Endpoint:

• Safety and Tolerability

Secondary Endpoints:

- Change in Eczema Area and Severity Index Score (EASI) from baseline to visit 8 EASI score will assess severity and extent of AD with respect to erythema, excoriation, infiltration and lichenification at 4 anatomic sites of the body: lower and upper extremities, trunk and head. The total EASI score shall be in a range (from 0 to 72 points (from no disease to maximum disease severity, respectively).
- Patients (%) achieving Investigator's Global Assessment (IGA) Response (0 or 1) at Visit
 - 8

IGA assesses disease severity and clinical response using a 5-point scale: 0 = clear; 1 = almost clear; 2 = mild; 3 = moderate; 4 = severe. The score is determined by ranking the extent of erythema and papulation/infiltration. A clinical response to therapy will be an IGA score of 0 (clear) or 1 (almost clear). Patients receiving more than one treatment with additional medication to treat AD exacerbation during the study or missing IGA scores at Visit 8 will be treated as non-responders.

- Patients (%) achieving ≥2 IGA Score Reduction at Visit 8
- Pharmacokinetics (PK) Assessment

An enzyme-linked immunosorbent assay (ELISA) has been developed to specifically measure bermekimab levels in human plasma. Blood will be drawn into a single 6 ml Na-Heparin collection tube at each PK collection time point (sample collection is pre-dose at visit 1, visit 3, visit 5, and visit 8). These samples will be collected per the study lab manual and immediately shipped to the Sponsor for PK analysis. The PK samples will also be used to test for the presence of antibodies against bermekimab.

- Change (%) for peak weekly averaged pruritus numerical rating scores (NRS) from baseline to visit 8
- The NRS rating system captures the intensity of patient's itch and pain over a 24-hour period. The following question will be presented to patients: "how would a participant rate his or her itch at the worst moment and on average during the previous 24 hours (scale 0 10 [0 = no itch; 10 = worst possible itch])?" and "how would you rate your pain on average during the previous 24 hours [0 = no pain; 10 = severe pain])?

```
CONFIDENTIAL
```

- Change in weekly averaged peak NRS from baseline to visit 8
- Change in SCORing Atopic Dermatitis (SCORAD) score from baseline to visit 8
 SCORAD was developed by the European Task Force on Atopic Dermatitis

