 - Visit 1 Questionnaire, Part 2: Pruritus, Pain and Erythema—data from this form must be recorded one hour post-injection (70 +/- 10 minutes)
- Adverse event monitoring

Visit 2 (Day 7 +/-2)

> At least 45 minutes before injection: When using pre-filled syringes, remove syringe from

refrigeration and lay flat; allow to warm to room temperature. Do not heat

Pre-injection

- o Concomitant medications/treatments
- o DLQI
- Urine pregnancy
- o EASI
- o IGA
- o HADS
- Pruritus/Pain NRS: data from patient diary to be recorded at this time if available
- o SCORAD
- o POEM
- o GISS
- Vital signs (blood pressure, pulse, oxygen saturation, respiratory rate and body temperature)

Bermekimab subcutaneous injection in accordance with injection site determined by BMI at Screening

Post bermekimab subcutaneous injection

- ➤ 1 hour monitoring post-injection
 - Injection reaction
 - Vital signs (blood pressure, pulse, oxygen saturation, respiratory rate and body temperature) one hour post injection (70 +/- 10 minutes)
- Adverse event monitoring

Visit 3 (Day 14 +/-2)

> At least 45 minutes before injection: When using pre-filled syringes, remove syringe from

refrigeration and lay flat; allow to warm to room temperature. Do not heat

Pre-injection

- Concomitant medications/treatments
- o DLQI
- Urine pregnancy
- o EASI
- o IGA
- o HADS
- Pruritus/Pain NRS: data from patient diary to be recorded at this time if available
- o SCORAD
- o POEM
- o GISS
- Blood draw:
 - chemistry and hematology, 12.5mL
 - PK and Biomarker Analysis, 6mL
- Vital signs (blood pressure, pulse, oxygen saturation, respiratory rate and body temperature)

Bermekimab subcutaneous injection in accordance with injection site determined by BMI at Screening

Post bermekimab subcutaneous injection

- ➤ 1 hour monitoring post-injection
 - Vital signs (blood pressure, pulse, oxygen saturation, respiratory rate and body temperature) one hour post injection (70 +/- 10 minutes)
- Adverse event monitoring

Visit 4 (Day 21 +/-2)

> At least 45 minutes before injection: When using pre-filled syringes, remove syringe from

refrigeration and lay flat; allow to warm to room temperature. Do not heat

Pre-injection

- Concomitant medications/treatments
- o Urinalysis
- o DLQI
- Urine pregnancy
- o EASI
- o IGA
- HADS
- Pruritus/Pain NRS: data from patient diary to be recorded at this time if available
- o SCORAD
- o POEM
- o GISS

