5.2 STUDY CALENDAR

Visit	Screen	1	2	3	4	5	6	7	8	9
Study Day		0	7 ±2	14 ± 2	21 ±2	28 ± 2	35 ± 2	42 ± 2	49 ± 2	56 ± 2
Informed Consent	Х									
Demography, Height, Weight ^f	х									
Medical History	х									
Infectious Disease Panel +	Х									
IGRA ^e	х									
Serum Pregnancy	Х									
Physical Examination	Х					Х			Х	Х
Urinalysis ▲		Х			Х				х	
Electrocardiogram (ECG)£		Х							Х	
Visit 1 Questionnaire ◆		Х								
Vital Signs ⁺	Х	Х	Х	Х	Х	Х	Х	Х	Х	Х
Urine Pregnancy		Х	х	Х	Х	х	Х	Х	х	
Blood Draw	x ^{ab}	x ^c		xabc		xabc			xabc	
Bermekimab Injection �		Х	Х	Х	Х	Х	Х	Х	Х	
EASI	Х	Х	х	х	Х	х	х	х	х	х
IGA	Х	Х	Х	Х	Х	Х	Х	Х	Х	Х
SCORAD	Х	Х	х	Х	Х	х	Х	Х	Х	Х
DLQI		Х	х	х	Х	х	х	х	х	х
Pruritus/pain NRS ^d		Х	Х	Х	Х	Х	Х	Х	Х	Х
POEM		Х	х	Х	Х	х	Х	Х	х	х
GISS		Х	Х	Х	Х	Х	Х	Х	Х	Х
HADS		X	х	X	Х	X	X	X	X	X
Adverse Events		Х	х	Х	Х	X	Х	Х	Х	х
Concomitant	X	X	х	х	X	х	X	X	Х	х
Meds/Treatments*										

^a Chemistry Panel including: Albumin, Alkaline Phosphatase, ALT, AST, GGT, Bicarbonate (CO2) Calcium,

Chloride, Creatinine, Glucose, Potassium, Sodium, Total Bilirubin, Total Protein, Urea Nitrogen

^b Hematology Panel including: Complete whole blood (WBC, HgB, Platelet, differential)

^cBlood draw for PK and Biomarker analysis

^d Data from patient diary for the previous 7 days to be recorded at this time.

^e Interferon gamma release assay

^fBMI will be calculated at this visit using height and weight

+HIV antibody, Hepatitis C antibody, Hepatitis B panel (HBsAg, anti-HBc, anti-HBs), and interferon gamma release assay (IGRA)

▲ Urinalysis will assess pH, protein, glucose, and blood cells

 \pounds A standard 12-lead ECG will be performed. The ECG strips and/ or reports will be retained with the source documentation.

✤ Each bermekimab injection will be followed by 1 hour monitoring for injection site reaction and vital signs 1 hour post injection (70+/- 10 minutes)

⁺ Vital signs include blood pressure, pulse, oxygen saturation, respiratory rate and body temperature

✦ Assessment of patients Pruritus, Pain and Erythema will be recorded twice [once pre-injection, once post-injection of bermekimab] during visit 1.

* Concomitant medications within 30 days before screening until 7 days after the last administration of the study drug must be recorded for the purpose of drug-drug and drug-disease interaction evaluation and signal detection.

BMI: Body Mass Index [BMI= weight (kg)/height (m²)]
IGRA: Interferon Gamma Release Assay
DLQI: Dermatology Life Quality Index

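### The adverse event table in 10.6.1 counts patients with a reaction over 4 injections in Group A and 8 in Group B, so for injection site reactions it mixes dose per injection with number of injections.

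*Combined protocol and SAP*

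**What the plan says.** Section 3.1 gives "Safety and Tolerability" as the only primary endpoint and does not define it further. Section 10.6 adds that "A summary of safety results will be presented for each treatment group".

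The Trial Design part of the synopsis sets the two regimens: "Group A (n=9): patients will receive a total of 4 X 200mg subcutaneous injections of bermekimab" and "Group B (n=20): patients will receive a total of 8 X 400mg subcutaneous injections of bermekimab". Section 2.6 gives 2 mL per injection in both groups, at 100 mg/mL in A and 200 mg/mL in B.

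Section 10.6.1 describes the adverse event tables: "The number and percentage of patients experiencing AEs and TEAEs will be summarized by seriousness (SAEs), severity (grades 1-5), SOC, and PT". Treatment-emergent events run from the first dose to the last study visit, which Section 3 places at 5 weeks in A and 8 weeks in B. Patient listings are also planned. There is no separate analysis of injection site reactions, no event count or rate per injection, and no window common to both groups.

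Section 9.7 lists injection site reactions as expected events, and the footnote to the Section 5.2 calendar makes each injection an observed opportunity for one: "Each bermekimab injection will be followed by 1 hour monitoring for injection site reaction and vital signs 1 hour post injection". Section 10.7.1 tabulates number of doses, dose volume and duration of exposure by arm, but does not use them as a denominator for adverse events.

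**The concern.** An injection site reaction can occur only after an injection. The percentage of patients who ever react therefore tends to rise with the number of injections, whatever the dose. In this design the higher-dose group also gets twice as many injections per patient. If B shows a higher percentage than A, the planned table cannot say whether 400 mg is less well tolerated per injection or whether B simply had more injections.

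Section 1.2 presents the study as dose ranging that will form the basis for later randomised studies. The side-by-side safety columns for the primary endpoint are the natural place for a reader to judge how tolerability changes with dose. At stake is how that descriptive table is read, not the validity of any test.

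**Working it through.** The plan states no power, event rate or sample-size formula, so there is no design figure to reproduce. Its one relevant rate does reproduce: 20/831 = 2.4% of patients with a reaction (Section 9.7).

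**Inputs from the documents**
- Group A: 9 patients × 4 injections = 36 planned injections.
- Group B: 20 patients × 8 injections = 160 planned injections.
- Summary measure: patients with at least one event, over the whole period.

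**Assumed input.** The risk p of a reaction per injection is not in the documents. The 2.4% is per patient, pools injection site with infusion reactions, and covers other indications. Read purely as a low anchor over four injections, it gives p = 1 − (1 − 0.0241)^(1/4) = 0.6%. The values 5% and 10% are illustrative.

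**Step 1: equal p in both groups, independent injections.** The expected percentage of patients with at least one reaction is 1 − (1 − p)^k, with k = 4 in A and k = 8 in B.

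| p | A (k = 4) | B (k = 8) | Ratio B/A |
|---|---|---|---|
| 0.6% | 2.4% | 4.7% | 1.98 |
| 5% | 18.5% | 33.7% | 1.81 |
| 10% | 34.4% | 57.0% | 1.66 |

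For example, at 5%: 1 − 0.95^4 = 0.185 and 1 − 0.95^8 = 0.337.

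**Step 2: reactions clustered within patients.** Let p vary between patients as a beta distribution with mean 5% and within-patient correlation r, so that a = 0.05(1 − r)/r and b = 0.95(1 − r)/r. The chance of no reaction in k injections is the product over j = 0 to k − 1 of (b + j)/(a + b + j).

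| r | A | B | Ratio B/A |
|---|---|---|---|
| 0.2 | 14.4% | 21.4% | 1.49 |
| 0.4 | 11.3% | 15.2% | 1.34 |
| 0.5 | 10.1% | 12.9% | 1.28 |
| 0.9 | 5.9% | 6.3% | 1.07 |

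For example, at r = 0.5, a = 0.05 and b = 0.95. For A the product is (0.95 × 1.95 × 2.95 × 3.95)/(1 × 2 × 3 × 4) = 0.899, which gives 10.1%. The excess vanishes only if the same patients react at every injection.

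**Step 3: what the table would show with 9 and 20 patients** (independent injections, equal p). At p = 5% the observed percentage is higher in B with probability 0.82. At p = 0.6% that probability is 0.51. The expected numbers of patients with a reaction are then 9 × 0.0238 = 0.2 in A and 20 × 0.0470 = 0.9 in B, and the chance of none at all in A is 0.994^36 = 0.81.

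**Step 4: the two aligned summaries at equal p.** Over injections 1 to 4, both groups have the same expectation: 18.5% at p = 5%, 34.4% at p = 10%. The probability that B is observed higher falls from 0.82 to 0.50 at p = 5%. Per injection given, p = 5% yields 1.8/36 and 8.0/160, both 5.0%.

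**The case against.** The strongest reply is that the plan makes no claim about dose differences in safety. Section 10.1 plans no hypothesis test for the primary endpoint, Section 10.2 says the sample is one of convenience, Section 10.5 is descriptive, and Section 10.5.4 rules out comparisons between dose groups (in the efficacy analysis). The percentage of patients who react over a whole regimen is a valid description of that regimen. The injection counts differ openly by design, and Section 10.7.1 will report doses by arm. Section 10 is also only the stated basis for the SAP, so some table detail may be left to it.

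Most of this stands. It is why the planned table should stay and why the point is about interpretation. It does not remove the point, because doses are never linked to reactions, and a summary devised after seeing open-label listings would be post hoc.

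A reader might infer more than the documents support:
- **That the plan builds in a false dose effect.** Nothing is tested, so there is no false-positive rate to inflate.
- **That the table will show B as worse.** This is an expectation. Step 3 shows how weak it is at low risk.
- **That the distortion is about twofold.** That holds only for low risk and independent injections. Both are assumptions, and strong clustering brings the ratio close to 1.
- **That the visit 3 procedure list adds to the imbalance.** The entry under "Visit 3 (Day 14 +/-2") in Section 5.1 has no injection reaction line, unlike the other injection visits. The gap applies to both groups, the visit still lists one hour of monitoring and adverse event monitoring, and the calendar footnote covers each injection. It is a separate inconsistency.

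**Conclusion.** The point holds as a limit on how the descriptive table can be read. For injection site reactions, the planned summary cannot separate dose per injection from number of injections, and nothing else in the plan does so. With equal per-injection risk the expected percentage is higher in B unless the same patients react every time.

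The size rests on assumptions. The excess in B is 2.3 percentage points at 0.6% per injection, 15.1 at 5% and 22.6 at 10% with independent injections. At 5% with a correlation of 0.9 it is 0.4 points. Full planned dosing is assumed throughout. No test or sample-size statement is affected, and with 9 and 20 patients the contrast between groups would be imprecise under any summary. Because the remedy is nearly free, it is worth making before the tables are fixed.

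**What to change.** Keep the planned table. Add to Section 10.6.1:

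1. The number and percentage of patients with an injection site reaction over injections 1 to 4, in both groups.
2. Injection site reactions per injection given in each group (planned denominators 36 and 160), with one overall interval per group that allows for clustering by patient. Do not plan intervals by grade or by injection number: with 36 injections in 9 patients most cells would be empty.

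The cost is two descriptive summaries from data already collected.

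Two separate minor points can be settled in the same revision. The visit 3 list in Section 5.1 and the calendar footnote in Section 5.2 disagree on the injection reaction check and must be reconciled. Treatment-emergent events could also be tabulated by relationship to study drug, which Section 9.5 already collects and on which rules in Sections 5.3, 5.5 and 5.6 depend.
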